#### Incidence of the other complications of liver cirrhosis during follow-up

The other complications (HE, gastrointestinal bleeding and HRS) will be analyzed as a composite event (the date of occurrence being the one of the first diagnosed complication) as well as separate events. The cumulative risk of other complications during follow-up in each group will be estimated by calculating the CIF at 12 months. The association of treatment group with the hazard function of other complications will be tested using univariate and multivariate Fine-Gray models. In this approach, death free of complications during follow-up will be considered as a competing event.

#### Number of days that patients spend in hospital during follow-up

Comparison between treatment groups will be performed with Student's t-test or the Mann- Whitney test, as appropriate.

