mortality rate by comparing two treatment strategies in "severe" cirrhotic patients with low protein level in ascites (< 15 g/L). Criteria of "severe" cirrhosis are the followings: 1) impaired renal function (serum creatinine  $\geq 106 \ \mu mol/L$ , uremia  $\geq 9 \ mmol/L$  or serum sodium  $\leq 130 \ mmol/L$ ) or 2) severe liver impairment (Child-Pugh score  $\geq 9$  with serum total bilirubin levels  $\geq 51 \ \mu mol/L$ ). The two proposed strategies will be to administer active or placebo rifaximin 550 mg x 2 / day for 12 months. Considering the probability of a noticeable survival benefit in the rifaximin arm, one interim analysis will be conducted, the significance boundaries being determined by a flexible alpha spending function. A total of 160 patients (80 per group) will permit to detect a 20% difference in the one-year mortality rate (60% in group with placebo versus 40% in the active rifaximin group), with a  $\beta$  error of 15% and a  $\alpha$  nominal inferior to 5% (2-tailed assumption) and considering that 10% of the patients may drop-out of the study follow-up. The inclusion period will be 48 months and 17 centers will participate.

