### Secondary objectives:

Demonstrate the effectiveness of rifaximin compared to placebo in reducing:

- Hospital mortality rate and mortality rate at 3 and 6 months
- Incidence of spontaneous ascites fluid infection at 12 months
- Incidence of other complications of cirrhosis (hepatorenal syndrome, gastrointestinal hemorrhage, hepatic encephalopathy) at 12 months
- Number of days spent in hospital during the follow-up period
- Analyze the safety of the drug under study
- Analyze the composition of the gut microbiota in 25 patients in each group (day 1, months 3, 6, 12 and 18).
- To show that rifaximin significantly decreases (compared to placebo) serum levels of IL-6, lipopolysaccharides (LPS), copeptin, von Willebrand factor antigen and CRP between J1 and J30.

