# 3.3 Sample size

The sample size is estimated based on a projected 40% survival rate at 12 months in the placebo group and 60% in the rifaximin group and a dropout rate of 10% at 12 months. In order to be able to detect any noticeable survival benefit in the rifaximin arm early in the trial, one interim analysis will be conducted. The significance boundaries of the interim and the final analyses were determined using a flexible alpha spending function (specifically alpha time (t2) spending function). This method ensures an alpha nominal risk inferior to 0.05 for the whole analysis.

We calculated that 160 patients (80 per group) would yield an 85% power in a two-sided test of hypothesis. The interim analysis will be performed when about 70% of the expected information is available (112 patients with complete follow-up), with a significance boundary p-value of 0.01. Consequently, the final analysis will have to be performed with a significance boundary p-value of 0.043. The estimated alpha nominal risk using these critical values will be 0.048. All sample size calculations were performed using PASS 14 software.

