### 5.2 Withdrawal/Follow-up

Criteria for stopping the study are:

• withdrawal of consent,

- liver transplantation,
- loss to follow up
- enrollment of ineligible subjects.

Patients withdrawn from the study for withdrawal of consent, liver transplantation or loss to follow up will be censored at the date of withdrawal. Ineligible subjects will be excluded from the mITT analyses.

For all other patients, monitoring of the patient will continue, follow-up will focus on collecting the endpoints of the trial:

- vital status,
- date of death,
- complications of liver cirrhosis (HE, gastrointestinal bleeding and HRS),
- dates and length of hospital stays during the 12 months following inclusion in the trial

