### Secondary endpoints

- Hospital survival and, 3- and 6-month survival
- Incidence of SBP during follow-up with date of diagnosis
- Incidence of the other complications of liver cirrhosis during follow-up (HE, gastrointestinal bleeding and HRS) with dates of diagnosis
- Number of days that patients spend in hospital during follow-up
- Safety analysis of the study drug
- The quantitative variations of IL-6, LPS, copeptin, CRP, vWF antigen in serum between day 1 and day 30
- The composition of the intestinal microbiota (quantity and quality of main bacterial strains) in 25 patients from groups A and B at day 1, and at months 3, 6, 12 and 18.

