#### Incidence of SBP during follow-up

The cumulative risk of SBP during follow-up in each group will be estimated by calculating the cumulative incidence function (CIF) of SBP at 12 months. The association of treatment group with SBP hazard function will be tested using univariate and multivariate Fine-Gray models. In this approach, death free of SBP during follow-up will be considered as a competing event.

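### Total hospital days are compared with no allowance for death, so under the planned survival benefit the result measures hospital burden and cannot be read as an effect on hospital use

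*SAP*

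**What the plan says.** SAP Section 2 lists among the outcomes that rifaximin is to be shown to reduce: "Number of days spent in hospital during the follow-up period". Section 6.1 repeats it as a secondary endpoint: "Number of days that patients spend in hospital during follow-up". Neither place gives a denominator or says what happens at death.

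The whole analysis in Section 6.2 is one sentence: "Comparison between treatment groups will be performed with Student's t-test", or the Mann-Whitney test where appropriate. Section 4.1 sets the two-sided 0.05 level for tests other than the primary one.

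Four other places bear on the point:
- Planned 12-month mortality (Background and Rationale) is "60% in group with placebo versus 40% in the active rifaximin group".
- Section 3.3 assumes "a dropout rate of 10% at 12 months".
- For SBP, "death free of SBP during follow-up will be considered as a competing event"; for the other complications, "death free of complications during follow-up will be considered as a competing event".
- Section 5.2 deals with early leavers in general: "Patients withdrawn from the study for withdrawal of consent, liver transplantation or loss to follow up will be censored at the date of withdrawal". Section 6.3 rules out imputation and uses observed values only.

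Section 5.2 also shows that vital status, date of death, and the dates and lengths of stays over 12 months are collected.

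**The concern.** A patient who dies in month 2 can add hospital days for two months at most; a patient who survives can add them for twelve. If rifaximin lengthens life as planned, its patients are at risk of admission for longer, and the raw total rises even when hospital use while alive is unchanged. In the other direction, if many deaths follow long final admissions, fewer deaths mean fewer terminal stays, and the total falls for that reason.

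So a higher, lower or unchanged total can each arise without any change in hospital use while alive. The stated aim is to demonstrate a reduction, and as written a reduction produced by earlier death would count as success. The primary conclusion on mortality is not affected.

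**Working it through.** The SAP gives no mean, SD or rate for hospital days, so it has no figure of its own to reproduce. The check starts from its mortality and dropout assumptions.

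**1. Time alive within 12 months.** With a constant hazard, λ = -ln(12-month survival) and mean days alive = 365.25 × (1 - e^-λ)/λ.
- Placebo, survival 0.40: λ = 0.9163; 365.25 × 0.60/0.9163 = 239 days.
- Rifaximin, survival 0.60: λ = 0.5108; 365.25 × 0.40/0.5108 = 286 days.
- Ratio 286.0/239.2 = 1.20.

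The ratio depends on when deaths occur. Weibull curves with the same 12-month survival give 1.12 (shape 2, later deaths: 278.7 against 311.5 days) to 1.29 (shape 0.5, earlier deaths: 203.1 against 261.8 days).

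**2. Adding 10% dropout.** Take an independent dropout hazard δ = -ln(0.9) = 0.1054.
- Mean follow-up becomes 228.8 against 272.7 days.
- The share leaving alive before 12 months is δ/(λ+δ) × (1 - e^-(λ+δ)): 6.6% and 7.9%, or about 5 and 6 of 80.
- The share with an observed death is λ/(λ+δ) × (1 - e^-(λ+δ)): 0.897 × 0.64 = 57.4% and 0.829 × 0.46 = 38.1%.

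**3. Direction of the effect on the mean.** Assume the same hospital rate in both arms.
- At 40 days/year, longer follow-up adds 40 × (272.7 - 228.8)/365.25 = 4.8 days per patient on rifaximin.
- If each death is preceded by a terminal stay of L days, fewer deaths remove (0.574 - 0.381) × L = 0.193 L days.
- The two cancel at L = 4.8/0.193, about 25 days. At 20 days/year they cancel at about 12 days, and at 60 days/year at about 37 days.

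This ignores the cutting of terminal stays in very early deaths. It shows that the sign turns on quantities the SAP does not give.

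**4. Effect on the test (simulation).** Inputs from the SAP: 80 per arm, 60% against 40% mortality, 10% dropout, two-sided 0.05. Assumed: equal hospital rates of 20-60 days/year in both arms, stays grouped into admissions with mean 8 days, and between-patient variation in the rate.

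| Terminal stays | Result | Mann-Whitney | t-test |
|---|---|---|---|
| None | More on rifaximin | about 11-27% | about 9-22% |
| 10-20 days | Either direction | often near nominal | often near nominal |
| 30 days, at 20 days/year | Fewer on rifaximin | about 14% | about 8-11% |

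With equal survival in the two arms, both tests stay near 5%.

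**5. A true effect can also be hidden.** With no terminal stays, a rate reduction of 1 - 239/286 = 16% would be fully offset by longer survival. Simulating a true 20% reduction (4 against 3.2 admissions/year, mean stay 8 days) gave mean totals of 20.2 against 19.3 days and rejection in about 5% of trials.

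**6. Early leavers.** Including or excluding the roughly 11 patients who leave alive early moves the difference in mean raw totals by less than 1 day.

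**The case against.** The strongest reply is that the planned test answers the question as worded. The objective and endpoint name days in hospital during follow-up, and the raw total is exactly that. Hospital use separate from survival is not an estimand the SAP claims. This stands: the test is not invalid for total burden and should be kept.

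A reader might infer that the SAP handles death properly for SBP and the other complications but forgets it here. The documents do not support that contrast. A cumulative incidence function with death as a competing event is itself a total-effect measure, in which early death lowers the incidence. A raw total to which the dead add nothing behaves in the same way.

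A reader might also infer that early leavers have no rule at all and that this matters. Sections 5.2 and 6.3, with the endpoint's own wording, most naturally mean counting stays up to leaving, and the choice hardly moves the raw difference. One sentence settles it.

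It is also true that mortality is reported in full as the primary endpoint, so a careful reader can set the two side by side. But nothing in the SAP tells the analyst to do so or to limit the claim.

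Finally, the scenario with no terminal stays is an extreme. The SAP makes hospital survival an endpoint and cites 20-30% hospital mortality for SBP, so some stays will end in death and the distortion may be small.

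**Conclusion.** The point holds as a minor one. The planned comparison of raw totals makes no allowance for death, while the objective speaks of demonstrating a reduction. The 239 against 286 days follows from the SAP's own mortality figures and constant hazards. Everything beyond that, including the sign, rests on assumed hospital rates, admission lengths and terminal stays.

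It would go too far to say that the test is biased for or against rifaximin in a known direction, since plausible inputs give either sign or almost no effect. The issue does not arise if survival is equal, and it touches one secondary endpoint only.

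**What to change.** In SAP 6.2, under hospital days:

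- **Add a supportive comparison** of days alive and out of hospital over the 12 months after randomisation, with days after death scored 0.
- **Keep the raw total and its test.** State that days are counted from randomisation to death, leaving the study or 12 months, whichever comes first. Label the result as total hospital burden, to be read beside mortality and not as hospital use independent of survival.
- **State how patients who leave alive early enter days alive and out of hospital**, with one simple sensitivity analysis. Extreme scoring is enough. At an assumed 40 hospital days/year the true difference is (286.0 - 239.2) × (1 - 40/365.25), about 42 days; counted only to leaving it is 43.9 × 0.89 = 39.1. Unobserved days average 14.1 (placebo) and 15.8 (rifaximin) per randomised patient, so the bounds are 39.1 - 14.1 = 25 and 39.1 + 15.8 = 55 days. Inverse-probability weighting is not needed for about 11 patients.

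The cost is a few lines of SAP text, one derived variable and one sensitivity analysis, with no new data. The downside is that days alive and out of hospital overlaps strongly with the primary endpoint: mortality alone made it significant in about 49-67% of simulated trials with equal hospital rates. It therefore prevents early death from counting as a good result, but it is not independent evidence of an effect on hospital use, and the SAP should say so.

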#### Variations of IL-6, LPS, copeptin, CRP, vWF antigen in serum between day 1 and day 30.

Differences in IL-6, LPS, copeptin, CRP, vWF antigen serum values between day 1 and day 30 will be calculated and difference means in each treatment group will be compared with Student's t-test or the Mann-Whitney test, as appropriate.

### Composition of the intestinal microbiota

To monitor changes in gut flora, 5 stool samples (day 1, M3, M6, M12, M18) will be collected. The composition of the intestinal microbiota (quantity and quality of main bacterial strains) will be analyzed and compared among 25 patients of each group. The patients' selection for this analysis will be performed as follows: 1) in the rifaximin arm, the 25 patients with the longer follow-up period will be retrospectively selected, 2) thereafter, 25 patients in the placebo arm will be selected by matching the follow-up period of the 25 patients selected in the rifaximin arm. In case of ties, a random drawing will be performed. These analyses, with their sample size estimation, have been placed under the responsibility of Pr [name], expert bacteriologist.

### 6.3 Missing Data

In general, missing values will remain as missing, i.e., no attempt will be made to impute missing values and only observed values will be used in data analyses and presentations.

### Survival analysis

All patients not reaching the primary endpoint at the end of follow-up or before their last assessment (for patients lost to follow-up) will be censored at the date of their last assessment visit. Patients receiving a liver transplant will be censored at the time of liver transplantation.

### 6.4 Harms

### Safety analysis of the study drug

Safety analyses will be conducted in the safety population using the same evaluation period as for efficacy analyses (i.e. from randomization until study end date).

The number of adverse events and SAE observed in each treatment group will be described and compared by using Chi-squared test or Fisher's exact test, as appropriate. Averse events will be described in a table in order of decreasing frequency.

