# **Section 4: Statistical Principles**

# 4.1 Confidence Intervals and P-values

The interim analysis was performed when about 70% of the expected information is available (112 patients with complete follow-up), with a significance boundary p-value of 0.01. Consequently, the final analysis will have to be performed with a significance boundary **p-value of 0.043**.

All other tests will be two-sided, with p values of 0.05 or less denoting statistical significance. 95% confidence interval will be used to report effect estimates of secondary endpoints.

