### Safety population

For each study drug, the safety population will include all patients exposed to at least one dose of said study drug.

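### The harms comparison tests numbers of adverse events with chi-squared or Fisher's exact test, without a patient-level unit and without allowing for the unequal observation time that the plan itself expects

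*SAP*

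**What the plan says.** SAP section 6.4 (Safety analysis of the study drug) specifies one between-arm comparison of harms: "The number of adverse events and SAE observed in each treatment group will be described and compared by using Chi-squared test". The section names Fisher's exact test as the alternative. The observation window is set "using the same evaluation period as for efficacy analyses", which the section spells out as randomization to the study end date. Section 4.3 defines the denominator group: "the safety population will include all patients exposed to at least one dose of said study drug". Section 4.1 makes the comparison a formal test: "All other tests will be two-sided, with p values of 0.05 or less denoting statistical significance".

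No section says that the unit is the patient with at least one event, and none gives a person-time denominator or a time-to-event method for harms. By contrast, section 6.2 analyses SBP and the other complications of cirrhosis with cumulative incidence functions and Fine-Gray models, treating event-free death as a competing event. Section 3.3 plans on 12-month survival of 40% with placebo and 60% with rifaximin, and 80 patients per group.

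**The concern.** There are two separate faults.

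**Repeated events.** A chi-squared or Fisher test needs independent units, each with a single yes/no outcome. Adverse events cluster within patients, and an event total has no binomial denominator. If the sentence is carried out as written, the variance is too small and the test rejects too often even when the drug does nothing.

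**Unequal observation time.** Follow-up for harms ends at death. If rifaximin prolongs survival as planned, its patients are observed longer and have more time in which to have an event. Totals, and the share of patients with at least one event, then differ between arms even when the event rate while alive is the same. Restating the unit as the patient does not remove this.

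At stake is the only formal safety comparison in the SAP. The primary endpoint is unaffected.

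**Working it through.** The SAP states no figure for the harms comparison, so there is none to reproduce.

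**Inputs from the SAP.** 80 per group; 12-month survival S of 0.40 and 0.60 (section 3.3); two-sided 5% tests (section 4.1).

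**Assumed, because the SAP gives none.** Exponential survival, follow-up ending at 12 months, no dropout; 1 to 6 events per patient-year; between-patient dispersion k from 0 to 1; the same true event rate in both arms.

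**Step 1: exposure.** Mean follow-up = (1 − S)/(−ln S).
- Placebo: 0.60/0.916 = 0.655 years.
- Rifaximin: 0.40/0.511 = 0.783 years.
- Ratio 0.783/0.655 = 1.20. With 10% dropout: 7.52 v 8.96 months, ratio 1.19.

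At equal rates, about 1.196/2.196 = 54.5% of events fall in the rifaximin arm.

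**Step 2: event totals.** The SAP does not say how a chi-squared test would be formed from totals. The natural version compares totals A and B with an equal split: (A − B)²/(A + B) against 3.84. Simulation with 80 per arm gives these rejection rates:

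| Events per patient-year | k | Equal survival (50% in each arm) | Planned survival |
|---|---|---|---|
| 1 | 0 | 6.8% | 17.8% |
| 1 | 1 | 16.6% | 26.0% |
| 2 | 0 | 8.7% | 30.6% |
| 2 | 1 | 26.3% | 39.9% |
| 4 | 0 | 12.6% | 48.5% |
| 4 | 1 | 38.9% | 53.5% |

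Up to 6 events per patient-year, the ranges are about 7% to 46% and 18% to 62%.

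Hand check for equal survival: the variance of a patient's count exceeds its mean by the factor φ = 1 + r[(1 + k)E(T²) − E(T)²]/E(T), where r is the event rate and T the follow-up time. With S = 0.5, E(T) = 0.5/0.693 = 0.721 and E(T²) = 2(1 − 0.5 × 1.693)/0.693² = 0.639. For r = 2, k = 1: φ = 1 + 2 × (1.277 − 0.520)/0.721 = 3.10, and rejection ≈ 2[1 − Φ(1.96/√3.10)] = 27%. For r = 1, k = 0: φ = 1.16, rejection ≈ 7%. Both agree with the table. Variable follow-up alone inflates the error, even at k = 0.

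**Step 3: patients with at least one event.** Chi-squared on this proportion rejects about 5% of the time with equal survival, but 10% to 22% under the planned survival. The reason can be seen directly. With death hazard λ and k = 0, the proportion is r/(r + λ) × [1 − exp(−(r + λ))]. For r = 2:
- placebo: 2/2.916 × (1 − 0.054) = 0.649;
- rifaximin: 2/2.511 × (1 − 0.081) = 0.732.

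The proportions differ although the rate is identical.

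**Step 4: rate per patient-year.** A log rate ratio with patient-level robust variance rejects about 5% to 6.5% of the time in both survival settings.

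**Step 5: direction if deaths count as SAEs.** Planned deaths are 80 × 0.60 = 48 and 80 × 0.40 = 32. Ratio of totals, rifaximin to placebo:
- 6 non-fatal events per patient-year: (375.9 + 32)/(314.3 + 48) = 1.13;
- 2: (125.3 + 32)/(104.8 + 48) = 1.03;
- 1: (62.6 + 32)/(52.4 + 48) = 0.94.

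**The case against.** The strongest reply is that the sentence is loosely worded rather than wrong. Section 5.3 names the same pair of tests for categorical patient variables, and a two-by-two table needs patients as its denominator, so the sponsor probably means patients with at least one event. That reading may well be what was intended, and it removes the repeated-event fault. But the SAP does not say so, and fixing the unit in advance is its job. The exposure fault survives this reading (Step 3).

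It is also fair to say that the test of totals in Step 2 is my construction and that the event rates and dispersion are assumed. The percentages therefore show what would happen under one natural execution of the literal text. They are not properties of a test that the SAP names.

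A reader might infer that an effective drug will look more harmful. The SAP does not support that as a general statement. It requires a survival difference, and for SAEs it also depends on whether deaths are counted, which section 6.4 does not say. If they are, the 20% excess shrinks and can reverse at low event rates (Step 5).

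Finally, section 6.4 ties no decision or stopping rule to these p-values, which limits the consequences.

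**Conclusion.** The concern holds in this form. As written, section 6.4 leaves the unit of the harms test open and, on its literal reading, treats repeated events as independent. On either reading it makes no allowance for the follow-up ratio of about 1.20 that the SAP's own survival assumptions imply.

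The rejection ranges in Steps 2 and 3 rest on the assumed event rates, dispersion and exponential survival. The smaller figures belong to low rates and no heterogeneity. With equal survival only the repeated-event fault remains, and it disappears if patients are the unit. The direction of the exposure bias for SAEs cannot be stated until the handling of deaths is fixed. The section should be corrected before the analysis.

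**What to change.** Amend section 6.4 as follows.

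- **Between-arm comparison:** event rate per patient-year, by negative binomial regression or Poisson regression with patient-level robust variance, with log follow-up time as offset. Do this separately for adverse events and SAEs. State whether deaths count as SAEs, and show fatal events separately.
- **Alternative:** cumulative incidence of the first event with death as a competing event, as section 6.2 already does for SBP and the other complications. This gives the absolute risk and handles censoring. But without dropout it equals the proportion in Step 3 at 12 months, so it still reflects longer survival. If this route is chosen, say so in the SAP and give the cause-specific hazard ratio beside it.
- **Descriptive reporting:** number and percentage of patients with at least one adverse event and at least one SAE, plus event totals, by arm. Label any Fisher's exact test on patients with at least one event as not adjusted for exposure.

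The cost is SAP wording and slightly more analysis of data already collected.

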# **Section 6: Analysis**

# **6.1 Outcome Definition**

### Primary endpoint

12-month survival. Death, whatever the recorded cause, will be considered as the primary endpoints. The date and, whenever possible, the causes of death will be recorded.

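### The SAE test in SAP 6.4 is not separated from the trial's efficacy events, so if those events count as SAEs a survival benefit can mask or reverse a real excess of other serious events

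*SAP*

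**What the plan says.** SAP section 6.4 (Harms) holds the whole safety analysis. On the comparison it says: "The number of adverse events and SAE observed in each treatment group will be described and compared", with a chi-squared or Fisher's exact test. On the period: "Safety analyses will be conducted in the safety population using the same evaluation period as for efficacy analyses", which runs from randomization to the study end date. The only breakdown by type is descriptive and is stated for adverse events: "Averse events will be described in a table in order of decreasing frequency". The section does not say whether patients or events are counted, and it makes no allowance for time at risk.

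The efficacy endpoints are defined in 6.1 and analysed in 6.2:
- Primary: "Death, whatever the recorded cause, will be considered as the primary endpoints".
- Secondary: "Incidence of SBP during follow-up with date of diagnosis".
- Also secondary: "The other complications (HE, gastrointestinal bleeding and HRS) will be analyzed as a composite event". Section 6.2 analyses these as separate events too.

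Drug safety is listed among the secondary objectives in Section 2. The SAP does not define an SAE and does not say whether endpoint events are counted as SAEs or exempted.

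**The concern.** Under the usual meaning of a serious event, a death is an SAE, and so are most episodes of SBP, HE, bleeding or HRS that lead to hospital admission. These are the outcomes that rifaximin is meant to reduce. A test on undivided SAEs would then mix the drug's intended effect with any harm it does. In a population with a planned one-year mortality of 40% to 60%, the intended effect could outweigh the harm.

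At stake is the safety objective. A successful trial could report fewer patients with SAEs on rifaximin while other serious events were more frequent, and the same benefit would be counted once as efficacy and again as safety. Counting each patient only once does not remove the problem.

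**Working it through.** **Inputs from the SAP.** 80 patients per arm and 12-month mortality of 60% on placebo and 40% on rifaximin (Section 2; section 3.3 gives the same as survival of 40% and 60%). The harms section gives no figure to reproduce. Dropout is ignored here.

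**Assumptions.** Deaths count as SAEs. The rates of non-fatal serious harm are illustrative, because the SAP gives none. The p-values are from the chi-squared test without continuity correction.

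**1. Deaths alone.** 80 × 0.60 = 48 on placebo and 80 × 0.40 = 32 on rifaximin, so 16 fewer patients with an SAE on rifaximin before any other event is counted (p = 0.011).

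**2. Patients with any SAE.** Let m be mortality and q the proportion with a non-fatal serious harm, taken as independent of death. Then P(any SAE) = 1 − (1 − m)(1 − q).

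Take q = 5% on placebo and 20% on rifaximin:
- Harm alone: 80 × 0.05 = 4 v 80 × 0.20 = 16, p = 0.004 (Fisher p = 0.007).
- Any SAE, placebo: 1 − 0.40 × 0.95 = 0.62, or about 50 patients.
- Any SAE, rifaximin: 1 − 0.60 × 0.80 = 0.52, or about 42 patients.
- Comparison of 50 v 42: p = 0.20, with the sign reversed.

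With other values of q:

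| q placebo v rifaximin | Harm alone | p | Any SAE | p |
|---|---|---|---|---|
| 5% v 15% | 4 v 12 | 0.035 | 50 v 39 | 0.080 |
| 5% v 20% | 4 v 16 | 0.004 | 50 v 42 | 0.20 |
| 5% v 25% | 4 v 20 | 0.0004 | 50 v 44 | 0.34 |

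The sign is reversed as long as 0.60(1 − q on rifaximin) exceeds 0.40(1 − q on placebo). With 5% on placebo, that holds until the rifaximin proportion reaches 1 − (0.40/0.60) × 0.95 = 37%; with 20% on placebo, until 1 − (0.40/0.60) × 0.80 = 47%.

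**3. Counting events instead of patients.** Assume exponential survival. Mean time at risk over 12 months is 12 × m / (−ln(1 − m)):
- Placebo: 12 × 0.60 / 0.916 = 7.86 months.
- Rifaximin: 12 × 0.40 / 0.511 = 9.40 months.

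The rifaximin arm has about 123 more patient-months (80 × the difference, before rounding). If the non-fatal SAE rate is the same in both arms, the total breaks even at 16 / 123 = 0.13 per patient-month:
- At 0.05 per patient-month: 48 + 31.4 = 79.4 v 32 + 37.6 = 69.6, lower on rifaximin.
- At 0.20 per patient-month: 48 + 125.7 = 173.7 v 32 + 150.3 = 182.3, higher on rifaximin.

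The total can therefore move either way with no difference in harm.

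**4. Would removing the deaths be enough?** No. Let a non-fatal serious event have the same constant hazard h per year in both arms, with death hazard λ = 0.916 or 0.511. The proportion with the event before death is h/(h + λ) × (1 − exp(−(h + λ))). With h = 0.255 this is 15.0% on placebo and 17.8% on rifaximin. Longer survival alone produces that gap, so the added comparison must allow for time at risk.

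**The case against.** **The SAE rule may be in the protocol.** The definition of an SAE, and any exemption of endpoint events, usually stand there, and the protocol is not at hand. If these events are exempt, the masking in steps 1 and 2 disappears. This stands, and it is why the point is conditional. A reader might infer that a survival benefit necessarily lowers the SAE total; the SAP does not support that.

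**The direction is not fixed.** This is right for event counts (step 3). Chi-squared and Fisher tests need independent units, so patients with at least one SAE is the more natural reading. On that reading, with equal hazards of other SAEs that are independent of death, lower mortality always lowers the proportion. Reversal still depends on the rates: 50% v 70% gives 1 − 0.40 × 0.50 = 80% v 1 − 0.60 × 0.30 = 82%, which is diluted but not reversed.

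**Harm is also examined elsewhere.** Adverse events are tested too and listed by frequency, and section 6.2 already analyses deaths and each complication by arm. A reader might infer that the SAE test is the only look at harm; it is not. But the list is descriptive, none is stated for SAEs, and the tested SAE quantity stays undivided.

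**Leaving events out has its own risk.** HE, bleeding or HRS could in principle include drug harm, and a split by cause of death would rely on causes that 6.1 records only when possible. Both points stand. They argue for keeping the all-SAE comparison and for leaving out all deaths regardless of cause.

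**Conclusion.** The point holds in conditional form. Section 6.4 does not separate the tested AE and SAE counts from the efficacy events. If deaths and the listed complications count as SAEs, a benefit of the planned size (48 v 32 deaths) is enough to mask or reverse a real excess of other serious events: on illustrative rates, 4 v 16 patients with harm become about 50 v 42 with any SAE. If events are counted, the bias can go either way, with a break-even near 0.13 non-fatal SAEs per patient-month.

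This rests on three assumptions: that endpoint events are reported as SAEs, that non-fatal harm is independent of death, and that survival is exponential (for the event totals). It does not affect the primary efficacy conclusion. Nor does it make the all-SAE comparison wrong in itself; that comparison is a legitimate overall description, but it does not serve the safety objective well on its own.

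**What to change.** In section 6.4:
1. State whether efficacy events count as SAEs, and that the unit is the patient with at least one event.
2. Keep the all-SAE comparison.
3. Add a between-arm comparison of patients with at least one SAE other than death (whatever the cause), SBP, HE, gastrointestinal bleeding and HRS.
4. Estimate it with allowance for time at risk. An exposure-adjusted rate (time to first such event, with follow-up ending at death) keeps longer survival from creating a false excess, so judge the arms on it. Cumulative incidence with death as a competing event gives the absolute risk, but as step 4 of the working shows, it still rises with longer survival and should be read beside the rate.

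The cost is one additional table and one flag in the safety dataset. Dates of death and of diagnosis of the complications are already collected, and no attribution of cause of death is needed. The events left out remain covered by the analyses in 6.2 and by the retained all-SAE comparison.
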